Neurochlore carried out the phase IIb dose ranging study assessing the efficacy and safety of Bumetanide 0.5, 1.0 and 2.0mg BID doses (oral liquid formulation) in male and female patients aged ≥ 2 to ≤ 18 years of age diagnosed with ASD according to DSM-IV-TR. The main objective of the study was to determine the optimal dose of bumetanide for the pivotal phase III study. The primary criterion was the CARS scale. Three bumetanide oral solution doses, 0.5-1-2mg administered twice a day, were tested over a 3 month-treatment period. Eighty eight patients were included in the study. Using a general linear model including baseline CARS value as covariate, the difference between bumetanide 0.5 mg BID and placebo was statistically significant in the FAS -3.06 (95% CI $=[-5.63 ; -0.49]$, $p = 0.015$). When the CARS score was evaluated for 73 out of 88 patients who had a CARS value at D90 (CARS completers analysis), the results were confirmed using the general linear model for the comparison between Bumetanide 0.5 mg BID and placebo with an estimated difference at -2.93 (95% CI $=[-5.57;-0.29]$, $p= 0.026$). Bumetanide also produced significant improvements over placebo on the secondary efficacy endpoints (SRS scale, CGI-scale). On a qualitative point of view, clinicians describe that children with bumetanide are more present, more open to the world, more attentive, more participative, more willing to exchange, less hyperactive, less aggressive, less agitated and less stereotyped. The children also look more at their interlocutor. The safety profile of Bumetanide was dose-related. The best tolerability profile was observed with the Bumetanide 0.5 mg twice a day, whereas an important number of adverse events and study withdrawals were observed with Bumetanide 1.0 and 2.0 mg twice a day. Considering the 0.5mg dose is effective and presented a better safety profile than 1mg and 2mg: this dose was retained for the phase III.

Taking into account these elements, bumetanide was proposed as the first candidate allowing treatment of ASD core symptoms in paediatric population.

On the 24th February 2017, Neurochlore and Les Laboratoires Servier' entered into an agreement for development and commercialisation of the bumetanide paediatric formulation in Europe. 'Les Laboratoires Servier' takes over the phase III development program.

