1.2.2. Type of randomisation

The treatment randomisation and allocation are centralised using an Interactive Response System (IRS) procedure. The treatment (bumetanide or placebo) is assigned at inclusion visit by a balanced, non-adaptive randomisation with stratification on country and gender.

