1.3. Determination of sample size

The sample size was estimated to meet the primary endpoint defined as the change in CARS2 from baseline to 6 months using a two-sided Student's test.

With a total of 170 patients, statistical significance should be established with a power of 90% and a type-one error of 0.05 for an effect size of 0.5 between groups.

Assuming around 15% prematurely withdrawal rate, the total number of patients to be included is 200.

Missing data will be imputed using a reference based multiple imputation with a jump-to-reference approach or a standard multiple imputation depending on the reasons of withdrawal. Simulations were carried out to evaluate the impact of this procedure on power under various scenarios. The results on 1000 simulations have shown that power does not drop under 80% in the worst-case scenario.

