Primary analysis: bumetanide will be compared to placebo on the primary efficacy endpoint in the RS, using a General Linear Model (see Appendix 5.1.1.1) including the fixed, categorical effect of treatment, gender and country as well as the continuous fixed covariate of baseline value.

GENERAL LINEAR MODEL (ANCOVA): change = baseline country gender treatment [1]

The assumptions underlying the model, as for instance, the normality and homoscedasticity of residuals and detection of outliers, will be checked.

Missing data handling:

- For all study premature withdrawals due to other reasons as well as for study premature withdrawals due to lack of efficacy or AE in placebo arm, missing data will be imputed in both arms using a multiple imputation based on similar patients in the same treatment arm (missing at random assumption).
- For study premature withdrawals due to lack of efficacy or AE in S95008 arm, missing data will be imputed using a reference based multiple imputation with a jump-to-reference approach (*missing not at random assumption*).
Missing data as well as data considered as missing for the primary analysis due to the strategy used to handle intercurrent event will be imputed in the same way.

Multiple imputation inference involves 3 consecutive phases.

1/ Imputation step:

A total of 100 imputed complete data sets will be generated.

The imputation step of missing data with a monotone pattern will be separated in several sequences:

- For all patients with study or drug premature withdrawals due to other reasons as well as for patients with study or drug premature withdrawals due to lack of efficacy or AE in placebo arm, the regression method (adjusted on the same covariates as the model [1] and considering all longitudinal data of planned visits) will be used to impute missing data (*i.e.* based on patient completers under corresponding treatment arm).
- For patients with study or drug premature withdrawals due to lack of efficacy or AE in S95008 arm, the imputation step will be done sequentially for each time point t separately (W4, W12 and W26) based on placebo patients with non missing data at the timepoint t . The regression method will be adjusted on the same covariates as model [1] except the treatment variable (which is a modified variable in order to consider the placebo data as reference for imputation) and considering all longitudinal data of planned visits up to timepoint t .

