3.4.2.2. Sensitivity analyses

- Unadjusted analysis:

The same primary analysis will be performed for the primary endpoint using a General Linear Model (ANCOVA) without any covariates. The following model will be considered instead of model [1]:

GENERAL LINEAR MODEL (ANCOVA): change = baseline treatment [2]

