3.4.2.3. Supplementary analyses

- Treatment policy estimand:

The primary analysis will be repeated for the primary endpoint using all CARS2 values reported regardless of occurrence of treatment discontinuation.

In case of CARS2 values are still missing, the same imputation process as in the primary analysis will be performed for these individuals.

- Hypothetical estimand based on Mixed-effects Model for Repeated Measures

A Mixed-effects Model for Repeated Measures (MMRM) (see Appendix 5.1.3) using the longitudinal data at each planned post-baseline visit of the double-blind period (W004, W012 and W026) will be performed as if patients had continued their randomised treatment. In this analysis, all data occurring after all intercurrent events will be considered as missing. The comparison associated with the analysis will be the contrasts between Bumetanide and placebo for the change from baseline to W026 of the CARS2 total score. The model will include the fixed, categorical effects of country, gender, treatment, visit, treatment by visit interaction, country by visit interaction and gender by visit interaction as well as the continuous, fixed covariates of baseline and visit-by-baseline interaction:

*MMRM: change at each visit = baseline country gender treatment visit treatment*visit baseline*visit country*visit gender*visit [4]*

Statistical elements: the following elements will be provided in a summary table:

- Estimate (standard error) of the difference between adjusted treatment arm means.
- Two-sided 95% CI of the estimate.

- W012 analysis:

The primary analysis will be repeated for the CARS2 total score expressed in term of change from baseline to W012.

- CARS2 responders analysis:

Definition:

CARS2 responders will be defined as patients having an improvement of at least 4.5 points in the CARS2 total raw score as compared to baseline (Jurek *et al.*, 2021).

Main Analysis:

CARS2 responders at W012 and at W026 will be analysed using a logistic regression model with the fixed categorical effect of treatment, country and gender.

Note: In case of a complete separation of data (zero cell count in a treatment group), only descriptive statistics will be provided. In case of quasi-completed separation of data, a logistic regression with penalized maximum likelihood will be used (see Appendix 5.1.4).

Missing data handling:

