5.1.4. Logistic regression

To analyse the CARS2 and CGI responders, a logistic regression model with the fixed categorical effect of treatment, country and gender will be used.

In case of quasi-completed separation of data with the model mentioned above, the following models will be tested sequentially, until no facing the warning anymore:

- A logistic regression model with the fixed categorical effect of treatment, pooled countries and gender
- A penalized logistic regression model with the fixed categorical effect of treatment, country and gender
- A penalized logistic regression model with the fixed categorical effect of treatment, pooled countries and gender.

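### The supplementary CARS2-responder model omits baseline CARS2, unlike the SAP's continuous CARS2 models; adding it is a cheap, optional improvement

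*SAP*

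**What the plan says.** A CARS2 responder is a child whose total raw score improves by at least 4.5 points from baseline (SAP 3.4.2.3). The model is stated there: "CARS2 responders at W012 and at W026 will be analysed using a logistic regression model with the fixed categorical effect of treatment, country and gender". SAP 5.1.4 repeats it for both responder endpoints: "To analyse the CARS2 and CGI responders, a logistic regression model with the fixed categorical effect of treatment, country and gender will be used". The three fallback models in 5.1.4 pool countries, penalise the likelihood, or do both. None adds baseline.

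Country and gender are the stratification factors; SAP 1.2.2 describes a "balanced, non-adaptive randomisation with stratification on country and gender".

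The continuous CARS2 models differ:
- The primary ANCOVA (3.4.2.1, model [1]) has baseline, country, gender and treatment. The treatment-policy and W012 analyses repeat it.
- The sensitivity analysis labelled as unadjusted (3.4.2.2, model [2]) drops country and gender but keeps baseline.
- The MMRM (3.4.2.3) lists its categorical effects "as well as the continuous, fixed covariates of baseline and visit-by-baseline interaction".

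Responder status is derived from the 100 imputed datasets. The output is an odds ratio with standard error and 95% CI. SAP 3.4.1 gives p-values to the primary analysis only. The SAP gives no reason for leaving baseline out.

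**The concern.** Response is computed from change in a score whose baseline value is recorded. If children with higher baseline scores tend to change more (or less), baseline carries information about who responds. A model without it has two separate consequences. In a single trial, a chance difference in mean baseline between arms passes into the odds ratio, upwards or downwards. Averaged over trials, the comparison has somewhat less power than one that uses baseline.

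The stakes are small. The analysis is supplementary, has no p-value and drives no decision.

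**Working it through.** **1. The plan's own figure.** Two-sided 5%, 90% power, effect 0.5 SD: n per arm = 2(1.960 + 1.282)²/0.5² = 84.1, so 85 per arm and 170 in total. Exact t-test power at 85 per arm is 0.8999. With 15% withdrawal, 170/0.85 = 200. This matches SAP 1.3 and does not depend on the responder model, for which the documents give no figure.

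**2. Inputs.** From the documents: 100 per arm, effect 0.5 SD, 15% withdrawal, threshold 4.5 points, 12 planned countries. Assumed: SD of change 4.3, placebo mean change -2 or -4, country sizes 40 down to 5, 80% boys, baseline N(40, 6) truncated to 34-60, and r, the size of the baseline-change correlation.

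The SD is only loosely anchored. The phase IIb interval in Protocol section 2 gives SE = (5.63 - 0.49)/(2 × 1.99) = 1.29. With an assumed 22 children per arm, SD = 1.29/√(2/22) = 4.3 (3.9 to 4.5 for 18 to 24 per arm). That study lasted 3 months and covered ages 2 to 18.

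**3. Chance imbalance in one trial.** At 100 per arm, 95% of imbalances lie within 1.96 × √(2/100) = 0.277 baseline SD. By hand, the shift in log odds ratio is about r × 0.277 × (log odds ratio per SD of change):
- r = 0.3: 0.3 × 0.277 × (0.863/0.5) = 0.14
- r = 0.5: 0.5 × 0.277 × (0.857/0.5) = 0.24

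Simulation (placebo -2) gave 0.14 and 0.26. An imbalance at the 95% limit therefore moves the current odds ratio from 2.37 to 2.06 or 2.72 at r = 0.3, and from 2.35 to 1.82 or 3.04 at r = 0.5. With baseline in the model the log odds ratio moves by 0.01. At r = 0 neither model moves.

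**4. Chance (%) that the 95% CI excludes 1, without → with baseline.** Complete data: 4000 trials per cell. Missing data: 1500 trials per cell, 15% missing at W026, half of the active-arm dropouts imputed by jump-to-reference (assumed), 20 imputations.

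| r | Complete, placebo -2 | Complete, placebo -4 | 15% missing, placebo -2 | 15% missing, placebo -4 |
|---|---|---|---|---|
| 0 | 78.6 → 78.2 | 79.9 → 79.8 | 69.5 → 69.1 | 68.7 → 68.7 |
| 0.3 | 79.4 → 81.2 | 79.7 → 81.5 | 70.4 → 72.5 | 69.5 → 72.1 |
| 0.5 | 78.8 → 85.0 | 80.7 → 86.5 | 67.3 → 75.3 | 71.4 → 76.4 |

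The Monte Carlo SE of each paired difference is 0.2 to 0.5 points (complete) or 0.3 to 0.9 (missing).

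A separate complete-data simulation (SD 4.4 or 6, no entry cut-off) gave -0.7 to -0.4 points at r = 0, +2.1 to +3.7 at 0.35 and +5.0 to +7.8 at 0.5, with null rejection of 5 to 6% under either model. A further run gave -0.7 to +0.2 at r = 0, +1 to +4 at 0.3 and +5.5 to +8 at 0.5. Together these support the rounded ranges of 1 to 4 points at 0.3 and 5 to 8 at 0.5.

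**5. Where the gain comes from.** The log-scale SE rises; the estimate rises more (placebo -2):
- r = 0.3: 0.863/0.312 = 2.77 becomes 0.921/0.326 = 2.83
- r = 0.5: 0.857/0.312 = 2.75 becomes 1.040/0.351 = 2.96

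**6. Separation.** The table and the separate simulation pool countries with fewer than 10 patients. The SAP does that only for imputation (5.1.2); in the responder analysis, pooled countries are a fallback (5.1.4). With the unpooled first-line model and the assumed country sizes, country-level separation occurs in roughly 20 to 30% of trials; with small countries pooled, in about 1 to 3%. Adding baseline changes neither rate.

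**The case against.** The best case for leaving the model alone is that nothing is broken. The odds ratio conditional on the stratification factors is valid under randomisation, and one rule serves both CARS2 and CGI responders. No p-value or decision rule is attached, so how often the CI excludes 1 is not a planned use of the result. All of that stands.

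The shifts are also modest against ordinary uncertainty. With SE 0.312, the 95% CI around 2.37 is exp(0.863 ± 1.96 × 0.312), about 1.29 to 4.37. The limit-of-range shifts are 0.14/0.312 = 0.45 SE and 0.26/0.312 = 0.83 SE, and the CI already allows for chance imbalance. Any imbalance would show in the baseline table (SAP 3.2.3), next to the baseline-adjusted effects on the CARS2 scale. This limits the stakes.

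The phase IIb analysis, described in the Protocol as "Using a general linear model including baseline CARS value as covariate", concerns a continuous score. It is not a precedent for a responder model.

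Two further defences do not hold. Defining response on change does not adjust the odds ratio for baseline, and neither does having baseline in the imputation model. The latter only means that baseline is available in every imputed dataset.

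The objection that r is unknown is correct. It makes the gain uncertain, possibly nil, against a loss under 1 point if r is 0.

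**Conclusion.** A cheap, optional improvement to a supplementary analysis, and not an error correction. Adding baseline would raise the chance that the CI excludes 1 by about 1 to 4 points at r = 0.3 and 5 to 8 at r = 0.5, with no gain or a loss under 1 point at r = 0. These sizes rest on assumed values for r, SD, placebo change and country sizes. The primary analysis, type I error and sample size are unaffected.

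A reader might infer three stronger things that the documents do not support:
- **That the planned odds ratio is biased or the SAP contradicts itself.** Randomisation protects the comparison, and a different covariate set for a different endpoint is not a contradiction.
- **That an imbalance would weaken the result.** It can move the odds ratio either way; the loss of power is an average over trials.
- **That adjustment would narrow the interval on the log scale.** The log-scale SE becomes larger, because the adjusted odds ratio is a different conditional quantity.

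**What to change.** Before unblinding:
- Add continuous baseline CARS2 total score to the CARS2-responder models at W012 and W026 in SAP 3.4.2.3, and to the CARS2 versions of the fallback models in 5.1.4.
- Label the odds ratio as conditional on baseline, country and gender.
- Keep the current model as a sensitivity row.
- Leave the CGI responder models unchanged: CGI-I is itself a rating of change and has no baseline value.

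The cost is one model term and one table row per visit. Section 5.1.4 would no longer have one common model for the two responder endpoints, and there is one more parameter to estimate. The new odds ratio lies further from 1 with a larger log-scale SE, so the label is needed to stop readers taking it for a larger treatment effect.

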3.4.3. Secondary efficacy endpoints

3.4.3.1. Social Responsiveness Scale

Definition: The main analytical approach will be defined as the change in SRS-2 total raw score from baseline to W026.

Main Analysis: A General Linear Model with the fixed categorical effect of treatment, country and gender as well as the continuous, fixed covariate of baseline will be used for the SRS-2 change from baseline in the RS.

GENERAL LINEAR MODEL (ANCOVA): $change = baseline\ country\ gender\ treatment$

Missing data handling: For missing data handling, the same approach as for the primary endpoint will be performed. Data considered as missing for the analysis due to the strategy used to handle intercurrent event will be imputed in the same way.

Statistical elements: the following elements will be provided in a summary table:

- Estimate (standard error) of the difference between adjusted treatment group means.
- Two-sided 95% CI of the estimate.

Supplementary analyses:

- W012 analysis:

The same analysis will be repeated for the SRS total score expressed in term of change from baseline to W012.

- Descriptive analysis:

The same approaches as for the primary endpoint will be performed for the SRS total score.

3.4.3.2. Clinical Global Impression ScaleDefinition:

- The main analytical approach will be defined as the CGI-I score at W026.
- Responders CGI will be defined as patients with the CGI-I equal to “much improved” or “very much improved”.

Main analysis: A Robust General Linear Model (RGLM) using a rank-based analysis (Wilcoxon scores) (see Appendix 5.1.1.2) with the fixed categorical effect of treatment, country and gender will be used for the CGI-I score at W026 in the RS.

RANK-BASED GLM: CGI-I score = country gender treatment

Missing data handling: for missing data handling, the same approach as for the primary endpoint will be performed (see Appendix 5.1.2).

Statistical elements: the following elements will be provided in a summary table:

- Estimate (standard error) of the difference between adjusted treatment arms medians.
- Two-sided 95% CI of the estimate.

Supplementary analyses:

- W012 analysis:

The RGLM will be repeated for the CGI-I at W012.

- CGI responders analysis:

CGI responders at W012 and W026 will be analysed using a logistic regression model with the fixed categorical effect of treatment, country and gender in the RS.

Note: In case of a complete separation of data (zero cell count in a treatment group), only descriptive statistics will be provided. In case of quasi-completed separation of data, a logistic regression with penalized maximum likelihood will be used (see Appendix 5.1.4).

Statistical elements: the following elements will be provided in a summary table:

- Estimate (standard error) of the odds ratio between treatment groups.
- Two-sided 95% CI of the estimate.

- Descriptive analysis:

The CGI-I, CGI-S and CGI responders will be summarized using descriptive statistics and graphs:

- During the double-blind period: number and percentage of patient at each planned visit (for CGI-I and CGI responders: W000+Day 17, W004, W008, W012, W016, W020 and W026 / for CGI-S: W012 and W026) and the value at each planned visit for the CGI-S will be described in the RS by treatment groups (S95008 VS placebo).

- During the open-label period: number and percentage of patient at each planned visit (W038 (only for CGI-I and CGI responders) and W052) and the value at each planned visit for the CGI-S will be described in the RSO for the Placebo/S95008 arm. Of note that only CGI-I compared to W026 will be considered.
- During the combined period: number and percentage of patient at each planned visit and the value at each planned visit for the CGI-S will be described in the RSC for the S95008/S95008 arm. Of note that only CGI-I compared to W000 will be considered.

Moreover, the CGI-I (compared to W052) will be described at the follow-up visit (WEND) during the open-label period in the RSO by treatment groups (S95008/S95008 vs Placebo/S95008).

The number and percentage of patients at each planned visit in the extension period for the CGI-I (of note that CGI-I compared to the inclusion in the extension period will be considered) will be described in the RS patients included in the extension period.

3.4.3.3. Vineland Adaptative Behaviour Scale II (VABS II)

Definition: The main analytical approach will be defined as the change in standard score of each domain from baseline to W026.

Main Analysis: A General Linear Model with the fixed categorical effect of treatment, country and gender as well as the continuous, fixed covariate of baseline will be used for the change in standard score of each domain in the RS.

GENERAL LINEAR MODEL (ANCOVA): $change = baseline\ country\ gender\ treatment$

Missing data handling: for missing data handling, the same approach as for the primary endpoint will be performed. Of note that there is only one post-baseline planned visit (W026) to consider.

Statistical elements: The following elements will be provided in a summary table:

- Estimate (standard error) of the difference between adjusted treatment arm means.
- Two-sided 95% CI of the estimate.

Supplementary analysis:

VABS II standard domains scores, and Adaptative Behavior Composite standard score will be summarized using descriptive statistics and graphs:

- During the double-blind period: baseline, W026 as well as change from baseline to W026 will be described in the RS by treatment groups (S95008 vs placebo).
- During the open-label period: OL baseline, W052 as well as change from OL baseline to W052 will be described in the RSO for the Placebo/S95008 arm.
- During the combined period: baseline, each planned post-baseline visit as well as change from baseline to each planned post-baseline visit will be described in the RSC for the S95008/S95008 arm.

3.4.3.4. Paediatric Quality of Life Inventory

Definition: the four dimensions (Physical, Emotional, Social and School), the physical* and psychosocial health summary scores, and the total score will be calculated.

*Note: the physical health summary score is in fact the same as the Physical domain score. Only the latest will be presented, with a note in the output mentioning that it is the same.

The PedsQL questionnaire has been already validated in children with chronic conditions (Varni *et al.*, 2003) and pediatric population with psychiatric disorders (Limbers *et al.*, 2011). The psychometric properties will be checked separately.

Analysis:

A General Linear Model with the fixed categorical effect of treatment, country and gender as well as the continuous, fixed covariate of baseline will be used for the change from baseline to W026 in the four dimensions, the physical and psychosocial health summary scores and the total score in the RS.

GENERAL LINEAR MODEL (ANCOVA): change = baseline country gender treatment

Missing data handling: missing data will be imputed using the multiple imputation approach (MI).

Statistical elements: the following elements will be provided in a summary table:

- Estimate (standard error) of the difference between adjusted treatment group means.
- Two-sided 95% CI of the estimate.

Supplementary analysis:

The four dimensions, the physical and psychosocial health summary scores and the total score will be summarized using descriptive statistics and graphs:

- During the double-blind period: baseline, each planned post-baseline visit (W004, W012 and W026) as well as change from baseline to each planned post-baseline visit will be described in the RS by treatment groups (S95008 vs placebo).
- During the open-label period: OL baseline, each OL planned post-baseline visit as well as change from OL baseline to each OL planned post-baseline visit (W030, W038 and W052) will be described in the RSO for the Placebo/S95008 arm.
- During the combined period: baseline, each planned post-baseline visit as well as change from baseline to each planned post-baseline visit will be described in the RSC for the S95008/S95008 arm.

